7.1 AFL

During AFL irradiation, protective safety goggles will be worn by investigators and patients. To alleviate pain, treatment areas will be numbed. Injection of local analgesic is associated with discomfort. AFL causes transient edema and redness lasting for 5-10 days. Clinical healing of AFL microwounds takes 4-7 days. Infection risk after AFL alone is <10%. Post inflammatory hypo/hyperpigmentation may occur, but usually resolves after 1-2 months. Scarring, most commonly after treatment on eyelids, neck or chest, is rarely reported after AFL.

7.2 Topical Cisplatin and 5-FU

Storage, handling, personal protective equipment and disposal of chemotherapeutics as outlined by hospital guidelines, will be followed. Neither cisplatin nor 5-FU will come in contact with mucus membranes.

The side effect profile associated with intravenous cisplatin+5-FU therapy is not anticipated, as neither cisplatin nor 5-FU has been detected in the blood of live pigs measured hourly from 0-5 hours, 48 and 120 hours after topical AFL-assisted cisplatin+5-FU exposure. In that study, treatment consisted of a similar schedule/dose applied over a significantly larger skin area (>100 cm²). In this study, negligible systemic drug exposure is thus expected, an element that will be reassessed in the described preliminary study. On the other hand, transient local effects are common and expected after AFL-assisted cisplatin+5-FU on skin, likely to resolve within 30 days. When administered alone, AFL+cisplatin caused redness and edema peaking 48 hours after topical exposure, followed by a healing response. Using the combination of AFL-cisplatin+5-FU, the anticipated pattern is an early inflammatory phase characterized by erythema, a necrotic phase characterized by skin erosion, and finally healing (re-epithelialization). Local treatment effects can

be notable with blistering/ulceration. Estimated incidences after topical treatment with the two drugs are:

- Mild to moderate erythema (94-100%)
- Mild to moderate edema (33-99%)
- Scabbing (50-95%)
- Erosion (50-95%)
- Hypo/hyperpigmentation resolved after 1-3 months (30%)
- Pruritus (20%)
- Erythema lasting greater than 12 weeks (5%)
- Exudate, bleeding or crusting (1%)
- Infection (1%).
- Allergy (1%)
- Temporary hair loss in the treated area (<1%)

Dihydropyrimidine dehydrogenase (DPD) deficiency is an extremely rare genetic condition that renders 5-FU toxic to affected individuals. Toxicity typically presents within 96 hrs of administration. While extremely unlikely to occur due to the uncommonness of the mutation and the minimal levels of 5-FU anticipated to permeate into the systemic circulation, investigators will stay vigilant about this potential risk.

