3.4 Summary of Outcome Measures and Methods

Outcome measures and methods/techniques are summarized below. Detailed descriptions are presented in Section 6 and Table 1 (Appendix 1).

Primary outcome:

To investigate tolerability of topical AFL-assisted cisplatin+5-FU therapy for BCC by evaluating:

- I. Severity and duration of clinical local skin reactions including erythema, edema, scabbing, flaking and pustulation assessed by a physician using an established 0-4 point scale (none, mild, moderate, severe) from 0-30 days post-treatment.

- II. Occurrence of side effects (prolonged erythema/edema, hyper/hypopigmentation, scarring and infection) up to 3 months post-treatment.

Secondary outcome:

- 1) To monitor BCC tumor size and clearance based on clinical assessments and dermoscopy, supported by non-invasive imaging techniques including dynamic optical coherence tomography (D-OCT), reflectance confocal microscopy (RCM), high intensity focused ultrasound (HIFU) and histological analysis up to 3 months post-treatment.

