5.2.4 Topical 5-Fluorouracil (5-FU)

After cisplatin removal, the well bandage is disposed of and a thick amount of Efudix® 5% 5-FU cream (Meda Pharmaceuticals A/S, UK) is applied to the entire test area (corresponding to up to 0.125 ml per cm² skin). After 5-FU application, transparent dermatological film (TegaDerm® film dressing, 3M Medical, MN, USA) is applied to the test area as an occlusive dressing. The cream is left on the skin until next control visit. Thus, on Day 1 and 5, Efudix cream is reapplied at the same dose. The cream is removed on Day 7 after AFL treatment.

STUDY SET UP	Visit 1 Screening	Visit 2 Treatment Day 0	Visit 3 Day 1	Visit 4 Day 5 +/- 2 days	Visit 5 Day 14 +/- 3 days	Visit 6 Treatment* Day 30 +/- 5 days	Visit 7 Month 3 +/- 5 days
Screening & enrolment							
Informed consent	✓						
Inclusion/exclusion criteria	✓						
Relevant medical history	✓						
Location of BCC	✓						
Pregnancy test when relevant		✓				✓	
Interventions							
AFL		✓				(✓)	
Apply topical cisplatin(60min)		✓				(✓)	
Apply 5-FU under occlusion		✓	✓	✓		(✓)	
Clinical LSR evaluation							
FDA-approved LSR scale		✓	✓	✓	✓	✓	
Clinical photos		✓	✓	✓	✓	✓	
Safety							
Clinical evaluation		✓	✓	✓	✓	✓	
Tumor size and clearance evaluation							
Clinical/dermoscopic photos		✓	✓	✓	✓	✓	
D-OCT		✓				(✓)	
RCM		✓					
HIFU		✓				(✓)	
Biopsy							✓

*Offered if BCC residual or recurrence; (✓): Treatment/technique can be relevantly applied if tumor residuals are identified clinically or by D-OCT/RCM and there is no crusting etc. LSR: Local skin reactions, RCM: Reflectance confocal microscopy, D-OCT: Dynamic optical coherence tomography

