6.1 Primary Outcome

Tolerability measured as:

I) Local Skin Reactions (LSRs)

Non-blinded, clinical evaluation of erythema, edema, flaking, crusting/scabbing and pustulation in treated areas will be performed by a physician using a FDA-approved 0-4 point LSR scale at Days 1, 5, 14 and 30 after AFL exposure (Appendix 1). Standardized,

clinical photographs are taken to document LSRs at each visit.

II) Side Effects

Non-blinded, clinical evaluation of prolonged erythema or edema, hyper- or hypopigmentation, scarring and infection will be evaluated up to 3 months after initial AFL treatment.

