6.3 Methods for Outcome Assessment

6.3.1 Clinical Evaluation and Digital Photography

Clinical evaluation of LSRs (erythema, edema, flaking, crusting/scabbing and pustulation) in treated areas will be performed by a non-blinded physician using a FDA-approved LSR scale at Days 1, 5, 14 and 30 after baseline. The scale assesses severity of individual LSR parameters on a 0-4 points scale: none, mild, moderate, severe. Tumor size (mm) and clearance (yes or no) will also be evaluated by standard clinical dermoscopy at Day 30 and Month 3 (Appendix 1). Digital photography using a Canon Camera will be performed prior to, during, after treatment, and at control visits under standardized conditions. All images are assigned an ID-number and anonymized.

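### Local skin reaction severity is a primary outcome, but worse reactions between the Day 1, 5, 14 and 30 scores have no planned record, so any stated peak severity is a lower bound

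*Combined protocol and SAP*

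**What the plan says.** Section 3.4 (Summary of Outcome Measures and Methods) makes "Severity and duration of clinical local skin reactions" the first part of the primary outcome, over 0 to 30 days. Section 6.1 has a physician score them "at Days 1, 5, 14 and 30 after AFL exposure", and Section 6.3.1 repeats those days. The study set-up table under 5.2.4 also ticks the scale at Day 0. It gives Day 1 no window, then "Visit 4 Day 5 +/- 2 days", Day 14 +/- 3 and Day 30 +/- 5. The scored items are erythema, edema, flaking, crusting/scabbing and pustulation.

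On the expected course, Section 7.2 states that, given without 5-FU, "AFL+cisplatin caused redness and edema peaking 48 hours after topical exposure, followed by a healing response". For the combination it says that "the anticipated pattern is an early inflammatory phase characterized by erythema, a necrotic phase characterized by skin erosion, and finally healing", without naming a peak day.

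Under 5.2.4 the 5-FU cream is reapplied on Days 1 and 5 and taken off on Day 7. The schedule has no Day 7 visit. Section 8.2 directs that reactions covered by the LSR scale are entered as LSRs rather than adverse events, even when they need treatment. The documents describe no diary, recall question or photograph between visits.

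**The concern.** The trial asks how severe the reaction gets, and it answers from four post-treatment days. The only peak time in the protocol lies between two of them, and drug exposure ends between the second and the third. A reaction that worsens and eases between visits leaves no trace in the LSR scores, and Section 8.2 removes the adverse event record as a second source for the same items.

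Section 11 says this combination has not been tried topically in patients before. Section 9.1 rests the benefit/risk judgement on tolerability, with no control arm. A reader of the report would naturally take the highest score seen as the worst the treatment does.

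**Working it through.** There is no sample size or power figure to reproduce; Section 9.1 says no formal calculation was made. The check compares the visit windows with the two time points that matter.

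**Windows (set-up table, 5.2.4), in days after AFL**
- Visit 3: Day 1
- Visit 4: 5 - 2 to 5 + 2 = Days 3 to 7
- Visit 5: 14 - 3 to 14 + 3 = Days 11 to 17
- Visit 6: 30 - 5 to 30 + 5 = Days 25 to 35

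**48 hours (Day 2; Section 7.2, without 5-FU)**
- Day 2 lies in none of these windows.
- Delay to the next score: 3 - 2 = 1 day at the earliest, 5 - 2 = 3 nominally, 7 - 2 = 5 at the latest.
- Unscored interval after Day 1: 3 - 1 = 2 days at the shortest, 5 - 1 = 4 nominally, 7 - 1 = 6 at the longest.

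**End of 5-FU exposure (Day 7; 5.2.4)**
- No nominal visit falls on Day 7. Visit 4 can, but only on the last day of its window.
- Gap from Visit 4 to Visit 5: 11 - 7 = 4 days at the shortest, 14 - 5 = 9 nominally, 17 - 3 = 14 at the longest.
- Delay from Day 7 to Visit 5: 11 - 7 = 4, 14 - 7 = 7 or 17 - 7 = 10 days.

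**Direction of the error.** Setting scoring error aside, the maximum over a few days cannot exceed the maximum over the whole period. An error in peak severity from this source can only be downward.

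**Size of the error.** The documents give no time course of scores, so it cannot be calculated. The figures below only show how missed reactions act in a group of 12. The true rate p of severe LSRs and the missed share m are assumptions. The chance of seeing no severe reaction in 12 patients is (1 - p(1 - m))^12.

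| p | m = 0 | m = 25% | m = 50% | m = 75% |
|---|---|---|---|---|
| 10% | 28.2% | 39.2% | 54.0% | 73.8% |
| 30% | 1.4% | 4.7% | 14.2% | 39.2% |

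For example, with p = 30% and m = 50%: (1 - 0.15)^12 = 0.142. Nothing in the documents says which column applies.

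**The case against.** Several stronger readings are tempting, and the case against them is good.

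- **The protocol expects this treatment to peak at 48 hours, unseen.** Not supported. The 48-hour figure is for a regimen without 5-FU. Under the combination, 5-FU stays occluded from Day 0 up to the Day 5 visit, and Section 7.1 expects redness and edema from AFL itself to last 5 to 10 days. A sharp rise and fall between Day 1 and Day 5 is possible, but nothing in the documents predicts it.
- **Nothing can be scored on Day 7.** Too strong. Visit 4 may fall on that day; it is only not scheduled there.
- **The late gap hides the erosion phase of the primary outcome.** Erosion is not a listed LSR item. The Section 8.2 exemption covers only reactions on the scale, so erosion can be recorded as an adverse reaction with start and end dates. The late gap concerns the five listed items.
- **The trial will report a biased maximum.** Section 9.3 plans medians or means and tests at time points; no maximum is defined. A score reported for its own day is not biased by an unobserved Day 2.
- **The decision to stop inclusion will be wrong.** Section 4 gives only an example, all patients having severe LSRs, and no numerical threshold.

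One can add that two scored control visits by Day 5 are reasonable for a small explorative study. All of this stands and limits the point. It does not supply a record of what happens to the listed items between visits.

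**Conclusion.** The point holds as a minor one. LSR severity is known only at the scheduled visits. No window covers 48 hours, no score is scheduled at the end of 5-FU exposure, and the nominal gap around that time is 9 days (range 4 to 14). Because LSR-scale reactions are not entered as adverse events, a worse reaction between visits has no planned record. Any claim about worst or peak severity can therefore only be too favourable, and by how much cannot be said.

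This rests on the windows as printed and on there being no assessment between visits beyond what the documents describe. It affects statements about peak severity, not the scores reported for each day. It does not show that the combination peaks on Day 2 or that severe reactions will be missed.

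**What to change.** Leave treatment and visits as they are.

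1. At Visits 4 and 5, add CRF items for the worst reaction since the last visit on each LSR-scale item, the day it occurred, and whether it needed treatment. Report these separately from the physician scores and do not merge them.
2. In Section 3.4 (Summary of Outcome Measures and Methods) and Section 6.1, state that severity is the score at scheduled visits, to be reported with the actual day of assessment, and that any maximum drawn from these scores is a lower bound for peak severity. Do not write a 48-hour peak into these sections as an expectation, since none is stated for the combination.

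The cost is a few CRF items at visits already planned, and some wording. The downside is that recalled severity is less exact than a physician's score, hence the separate reporting. A patient photograph on Day 7 is not advised, because the documents do not say who removes the cream. If only one change is made, the wording in item 2 costs least and prevents the scores from being over-read.

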4.1 Inclusion criteria

Subjects who meet all of the following criteria are eligible to participate in this study:

1. Histologically-verified, previously untreated superficial or nodular BCCs on the scalp, face, extremities or trunk
2. >18 years of age at baseline
3. Legally competent, able to give verbal and written informed consent
4. Subject in good general health, is willing to participate and can comply with protocol requirements.
5. Fitzpatrick skin phototype I-III
6. Female subjects of childbearing potential¹ must be confirmed not pregnant by a negative urine pregnancy test prior to trial treatment.

¹Female subjects are considered of childbearing potential unless they have been hysterectomized or have undergone tubal ligation or have been post-menopausal for at least one year prior to first visit.

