4.2 Exclusion criteria

Subjects meeting any of the following criteria are not eligible to participate in this study:

1. High-risk BCC
 - i. Tumors in the following anatomical locations: midface, orbital, ears
 - ii. Size: >20 mm in facial/scalp areas or > 50 mm in non-facial/non-scalp areas
 - iii. Subtype: morpheaform and micronodular BCC
 - iv. History: Gorlin syndrome or immunosuppression
2. Previous treatment of the BCC lesion
3. Known allergy to cisplatin or Efudix®
4. Other skin diseases present in the treatment area
5. Tattoo in the treatment area which may interfere with or confound evaluation of the study
6. History of keloids which is deemed clinically relevant in the opinion of the investigator
7. Fitzpatrick skin phototype IV-VI
8. Lactating or pregnant women

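### Section 7.2 names DPD deficiency as making 5-FU toxic, but section 4.2 does not exclude a patient known to have it, and the 96-hour statement is not reconciled with the visits after the Day 5 application and the Day 30 course

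*Combined protocol and SAP*

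**What the plan says.** Section 7.2 (Topical Cisplatin and 5-FU) identifies one group for whom the study drug is a particular hazard: "Dihydropyrimidine dehydrogenase (DPD) deficiency is an extremely rare genetic condition that renders 5-FU toxic to affected individuals". It adds: "Toxicity typically presents within 96 hrs of administration". Its reason for accepting the risk is: "While extremely unlikely to occur due to the uncommonness of the mutation and the minimal levels of 5-FU anticipated to permeate into the systemic circulation". Its stated response is that "investigators will stay vigilant about this potential risk".

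Section 4.2 lists eight exclusions. The only one tied to the study drugs is "Known allergy to cisplatin or Efudix". The nearest general criterion in section 4.1 is "Subject in good general health, is willing to participate and can comply with protocol requirements". Neither list mentions DPD.

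The first application of 5-FU is on Day 0. Section 5.2.4 then says: "Thus, on Day 1 and 5, Efudix cream is reapplied at the same dose", and "The cream is removed on Day 7 after AFL treatment". The schedule table there places visits on Day 1, Day 5 (± 2 days), Day 14 (± 3 days), Day 30 (± 5 days) and Month 3 (± 5 days). Section 3.3 allows a repeat course on Day 30 if tumor persists.

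**The concern.** The protocol recognises a specific hazard in its risk section but does not carry it into the criteria that decide who is treated. An enzyme deficiency is not an allergy, and a patient with no symptoms of it can be in good health. Three other places that might catch a known case do not clearly do so:

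- The screening row for relevant medical history has no defined content.
- Section 10.2 limits record access to investigations and treatments of the BCC, up to 4 months from inclusion.
- Section 4.4 allows withdrawal when an exclusion criterion emerges during participation, but DPD deficiency is not such a criterion. If it came to light before the Day 30 course, only general medical judgment would remain.

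The promised vigilance is also not tied to a particular assessment. The safety row of the schedule reads only as a clinical evaluation, and blood is drawn once, at 24 hours, in up to 6 preliminary-study patients (section 3.5).

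Patient safety comes first here. There is also a consequence for interpretation: section 9.1 frames the primary objective around severe or serious related events in 24 subjects. One avoidable systemic event would be 1/24 = 4.2% of the trial, or 1/12 = 8.3% of a tumor-type group.

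**Working it through.** **Eligibility.** The sections can be set side by side.

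- Section 7.2: DPD deficiency makes 5-FU toxic.
- Section 4.1: no DPD criterion.
- Section 4.2: no DPD criterion.
- Schedule table: no DPD item beyond general medical history.

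A patient with a known deficiency who meets everything else is therefore eligible as written. The two reasons given in section 7.2 do not change this. Rarity bears on whether to look for unknown cases. Minimal uptake is an expectation that section 7.2 itself says will be reassessed in the preliminary study, and section 11 says this combination has not been tested in patients before.

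**Timing.** Inputs are the 96 hours from section 7.2, and the application days and visit windows from section 5.2.4. The formula is hours = (visit day − application day) × 24. The range uses the limits of the windows. Month 3 is taken as Day 90, which is an assumption.

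| Application | Visit | Nominal hours | Range across windows | Nominally within 96 h? |
|---|---|---|---|---|
| Day 0 | Day 1 | (1 − 0) × 24 = 24 | 24 | Yes |
| Day 0 | Day 5 | (5 − 0) × 24 = 120 | 72–168 | No |
| Day 1 | Day 5 | (5 − 1) × 24 = 96 | 48–144 | Yes, exactly |
| Day 5 | Day 14 | (14 − 5) × 24 = 216 | 96–336 | No |
| Day 30 | Month 3 | (90 − 30) × 24 = 1,440 | at least (85 − 35) × 24 = 1,200 | No |

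The Day 5 application reaches 96 hours only in the extreme case of Visit 4 on Day 7 and Visit 5 on Day 11: (11 − 7) × 24 = 96. Counting from removal of the cream on Day 7 does not alter the conclusion, since (14 − 7) × 24 = 168 hours to nominal Day 14.

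So two of the three first-course applications have a nominal visit within the protocol's own window. The third application and the repeat course have none. The documents do not say whether the Day 1 and Day 5 reapplications are repeated after Day 30; the schedule shows no visits for them.

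No sample size, power or alpha figure bears on this point.

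**The case against.** The strongest case against runs as follows. The protocol names the risk, calls it extremely rare and gives reasons for accepting it. The pig study, with a similar schedule and dose over more than 100 cm², found no detectable drug in blood hourly to 5 hours or at 48 and 120 hours. An earlier report cited in the background describes 28 patients given laser-assisted 5-FU under 7-day occlusion without adverse effects. The physicians told to be vigilant work in the team that takes the history, and eligibility does not oblige them to enrol anyone. Section 8 promises close follow-up in the first 30 days, and toxicity that appears within 96 hours may still be visible at a later visit.

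Much of this stands, and it rules out several stronger readings that a reader might infer.

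- *That the vigilance has no visit to support it.* It has: Day 1 and Day 5 are safety visits during exposure, and section 3.3 puts a skin evaluation before each reapplication.
- *That a site must accept a known case, or that section 4.2 bars nothing but allergy.* The criteria permit enrolment without compelling it, and seven other exclusions are listed.
- *That the applied amount shows systemic risk.* The largest eligible lesion, 50 mm plus a 5 mm margin on each side and assumed circular, gives π × 3.0² = 28.3 cm². At the background's 6.25 mg/cm² this is 177 mg per application and 530 mg over three. That is a ceiling on drug applied, not drug absorbed. A 20 mm facial lesion gives π × 1.5² = 7.1 cm², or 44 mg per application. The pig area was at least 100/28.3 = 3.5 times the largest of these.

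What the objection does not answer is why a known case should remain eligible. The protocol does not say that the pig data or the 28 patients address DPD deficiency. The single human blood sample at 24 hours comes before the Day 5 application, so it cannot describe the full 7-day exposure.

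**Conclusion.** The point holds in two limited parts. First, sections 7.2 and 4.2 are not reconciled: a patient known to be DPD-deficient may be enrolled on the criteria as written. Second, the 96-hour statement and the promised vigilance fit the schedule after the Day 0 and Day 1 applications, but not after the Day 5 application (nominally 216 hours to the next visit) or the optional Day 30 course (about 1,440 hours).

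The second part assumes that Month 3 means Day 90, that no unscheduled contacts are counted, and that hours run from each application. The first part needs no assumption about prevalence, and the documents give none.

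This is a modest, inexpensive safety gap. It is not a numerical error or a flaw that undermines the trial. The documents do not show that systemic toxicity is likely, and nothing here implies that all patients should be tested.

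**What to change.** Reconcile section 4.2 with section 7.2 by adding known DPD deficiency to the exclusion list, and ask about it within the medical history already taken at Visit 1. The cost is one line of text and one screening question, with practically no loss of patients given how rare the protocol says the condition is.

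Separately, the protocol authors must reconcile the 96-hour statement and the promised vigilance in section 7.2 with the schedule in section 5.2.4, for the period after the Day 5 application and after the optional Day 30 course. How to do so is a clinical decision for them; no visit time or management rule is proposed here. The cost of that part depends on the solution chosen.
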